10.2 Number of Subjects to be enrolled

The study will be a Phase I trial to assess the technical feasibility of generating Tregs from the thymus in the GMP facility and most importantly their safety in the treatment of paediatric heart transplant patients.

In this study we will determine the optimal dose of injected Tregs using a single ascending dose (SAD) design, with groups of three patients. We will enrol 3 patients with the first low dose of $(1-3 \times 10^6 \text{ Tregs/Kg})$ and if safe, then another 3 will be added with the second higher dose of $(5-10 \times 10^6 \text{ Tregs/Kg})$. If the previous dose was safe, an additional 3 patients will be enrolled with the highest tolerated dose to test further the biological activity.

The first patient in the first cohort (Cohort 1) will receive the treatment and we will confirm the safety of the infused cell product following the treatment before infusing the next patient with at least a 4-week gap. After safety is confirmed for the first patient, the second and third patients within Cohort 1 will receive the same dose of treatment. A safety review will be done after the third patient to decide the dose for the next cohort (Cohort 2). The same process will be done for the next cohorts (Cohort 2 and Cohort 3). This will allow us better to capture the safety of the product and biological activity at the selected dose in a robust manner and also to provide information on the immunological effects of the Treg product.

To determine the maximum tolerated dose (MTD) of the two potential doses, a 3+3 dose escalation design will be implemented. A 3+3 dose escalation design assesses cohorts of patients for dose-limiting toxicities (DLTs) in order to make a decision about maintaining the dose level, increasing the dose level or stopping the trial using a rule base approach. Initially a cohort of 3 patients will be administered TR006 with the dose level of $1-3 \times 10^6$ Tregs/Kg.

The diagram below (Figure 1) describes the decision-making process for proceeding with the next dosing cohort based on the DLTs experienced. If a DLT occurs in the Cohort 1, the next cohort of 3 patients will be administered to the same dose. If there is no DLT in Cohort 1, another cohort of 3 patients will be administered to next higher dose. From this study design, the trial will be stopped when 2 patients out of 6 receiving the same dose level experience a DLT. At this point, either a MTD will be identified (green endpoints in diagram) or the trial will be stopped for safety (red endpoints in Figure 1).

Based on this study design, a sample size of between 9 and 12 patients will be needed to identify the maximum tolerated dose. The 3+3 design requires that 6 patients are dosed at the selected dose level, this is often a requirement of adaptive design approaches as well (see Figure 1 below). These 6 patients dosed at the final selected dose level will provide useful information on haematological activity which will be expanded upon with the inclusion of additional patients.

Figure 1: DLT decision-making process

A DLT is defined as grade ≥ 2 CRS, grade ≥ 2 injection site reaction, grade ≥ 2 fever and/or rigors, grade ≥ 3 bronchospasm or grade ≥ 3 hypoxia occurring within the first 72 hours post infusion OR a grade ≥ 3 infection, moderate or severe acute rejection (as defined by the ISHLT criteria grade II-III), grade ≥ 3 haematological complication considered to be related to Treg infusion or any grade ≥ 3 toxicity not clearly related to underlying disease occurring within 4 weeks post TR006 infusion (see Section 5.1 for full definition). [38]

For the purposes of the primary endpoint regarding safety, any DLTs after the TR006 administration will be reported and compared.

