2.1 Rationale for the study design

In this study we aim to conduct a Phase I clinical trial to assess the safety and feasibility of *in vitro* expansion of thymus-derived Tregs derived from explanted thymic tissue during surgery (or at the time of having a pump assist device fitted) and infusing them into 9 paediatric cardiac transplant recipients as a potential treatment to prevent CAV.

The first patient in Cohort 1 will receive TR006 and we will confirm the safety of the infused cell product following the treatment before infusing the next patient with at least a 4-week gap. Safety data that spans first four weeks post-dose will be made available from the database to the Data Monitoring Committee (DMC) who will assess this information to determine if the study can proceed with further recruitment and treatment.

After safety is confirmed for the first patient, the second and third patients will receive the same dose of TR006. A safety review will be done after the third patient to decide the dose for the next

cohort (Cohort 2). The same process will be done for the next cohorts (Cohort 2 and Cohort 3). A 3+3 strategy is employed to allow for expansion of the lower dose cohort in the event of any DLT or to allow for the higher dose cohort to begin sooner if there are no DLTs experienced at the lower dose.

In vitro cellular assays of anti-donor alloreactivity before and after Treg infusion will provide surrogate indicators of potential efficacy in promoting immune tolerance to the transplant antigens. The proposed research will yield valuable data on the applicability and safety of thymic Tregs for adoptive cell therapy in paediatric heart transplant patients. Results from this study will determine the optimal dose of injected Tregs. This will give the opportunity to test our strategy in a Phase II clinical trial where a larger cohort of patients will be tested. In addition, this will provide the opportunity to involve new national and international transplant centres for creating a consortium aiming to evaluate the efficacy of Treg therapy in children receiving heart transplant.

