5.1 Description of study design

This is a dose escalation, 3+3, open label, Phase I, single centre-trial investigating the safety and feasibility of two doses of autologous thymus derived regulatory Tregs (TR006) infused into 9 paediatric heart transplant patients.

We will enrol 3 patients at the first low dose of $1-3 \times 10^6$ Tregs/Kg (Cohort 1). The first patient in this cohort will receive the treatment and the safety of the infused cell product will be confirmed before infusing the next patient (with at least a 4-week gap). After safety of the treatment is confirmed for the first patient, the second and third patients of this cohort will receive the same dose of TR006 as and when this is possible. A safety review will be carried out after the third patient is treated to then decide to dose for the next cohort.

If safe, then another 3 patients (Cohort 2) will be treated with the second higher dose of 5-10 x 10^{6} Tregs/Kg. Similarly, the first patient in this cohort will receive the treatment and the safety of the infused cell product will be confirmed before infusing the next patient (with at least a 4-week gap). After safety of the treatment is confirmed for the first patient, the second and third patients of this cohort will receive the same dose of TR006.

A safety review will be performed after the third patient dosed as part of Cohort 2. If safe, a final 3 participants (Cohort 3) will be enrolled into the study to be treated at the highest tolerated dose (using the same dosing/safety review strategy as described for Cohort 1 and Cohort 2).

The study will determine the optimal dose of injected Tregs using a single ascending dose (SAD) design with groups of 3 patients in 3 cohorts (total of 9 patients that could be expanded to 12 in case of dose limiting toxicities). However, if a dose limiting toxicity (DLT) is observed in at least 1/3 in Cohort 1, this will result in expanding the low dose to Cohort 2 instead. A final 3 participants (Cohort 3) will be enrolled at the highest tolerated dose to test further the biological activity subject to there being no further DLTs observed at the low dose if expanded to Cohort 2 i.e. no more than 1/6 DLT or there are no more than 1/3 DLTs observed if Cohort 2 was escalated to the high dose.

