If both doses are tolerated, there will be a total of n=9 patients in the study (3 at the low dose and 6 at the high dose or 6 at the low dose and 3 at the high dose). If the higher dose can only be assessed from Cohort 3 and there is 1/3 DLT observed, a further 3 patients will need to be treated at this dose to establish the highest tolerated dose. In this scenario, funding for a further 3 participants will be applied for and the total sample size will be 12 participants.

A DLT will be determined from data collected during the 4-week period post TR006 infusion. Patients with no undue toxicity will be managed and continued on therapy. A DLT will be graded according to the National Cancer Institute's Common Terminology Criteria for Adverse Events (CTCAE) on a 1 to 5 sale as follows [37]:

Grade 1: Mild adverse event Grade 2: Moderate adverse event Grade 3: Severe and undesirable adverse event Grade 4: Life-threatening or disabling adverse event Grade 5: Death.

A DLT is a toxicity considered to be related to TR006. The following events will be considered DLTs:

Occurring in the first 72 hours post infusion:

- CTCAE ≥ grade 2 cytokine release syndrome
- CTCAE ≥ grade 2 injection site reaction
- CTCAE ≥ grade 2 fever and/or rigors
- CTCAE ≥ grade 3 bronchospasm
- CTCAE \geq grade 3 hypoxia

Occurring in the first 4 weeks post TR006 infusion:

• CTCAE \geq grade 3 infection

• Moderate or severe acute rejection (as defined by the International Society for Heart and Lung Transplantation (ISHLT) criteria grade II-III) [38]

- CTCAE \geq grade 3 haematological complication (neutropenia, thrombocytopenia, anaemia).
- Any CTCAE ≥ grade 3 toxicity not clearly related to underlying disease

6 Population

9 paediatric patients on the heart transplant register at GOSH will be recruited to the study.

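### Section 10.2 states 9 to 12 patients and six at the selected dose; the decision rules in section 5.1 guarantee neither

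*Protocol*

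**What the plan says.** Protocol section 10.2 gives the sample size as a property of the design: "Based on this study design, a sample size of between 9 and 12 patients will be needed to identify the maximum tolerated dose". The next sentence adds: "The 3+3 design requires that 6 patients are dosed at the selected dose level".

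The rules that produce the numbers are these:

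- **No DLT in Cohort 1 (low dose, three children).** Section 10.2: "If there is no DLT in Cohort 1, another cohort of 3 patients will be administered to next higher dose". The low dose then stays at three.
- **A DLT in Cohort 1.** Section 5.1, on a DLT "observed in at least 1/3 in Cohort 1, this will result in expanding the low dose to Cohort 2 instead".
- **Opening Cohort 3.** Section 5.1 allows it if the expanded low dose has at most 1/6 DLT, or if "there are no more than 1/3 DLTs observed if Cohort 2 was escalated to the high dose".
- **Final state when both doses are tolerated.** Section 5.1 gives nine patients: "3 at the low dose and 6 at the high dose or 6 at the low dose and 3 at the high dose". Three more are added at high only when high is first given in Cohort 3 and shows 1/3 DLT, for a total of 12.
- **Stopping.** Sections 10.2 and 10.4 stop the trial at two DLTs among six at one dose and refer to Figure 1 for the endpoints.
- **Cohort 3 in section 2.2.** Three more patients are enrolled at the highest tolerated dose. The section does not say what happens if high has failed in Cohort 2.

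Section 2.1 states the purpose: "Results from this study will determine the optimal dose of injected Tregs".

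**The concern.** Section 10.2 tells a reader that whichever dose is carried forward will have been given to six children, and that nine is the smallest trial that can identify it. Section 5.1 accepts an outcome with three children at the high dose. It also contains routes on which the low dose is the only one left and has been given to three.

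The data monitoring committee applies these rules, and the result is meant to feed a Phase II trial. A dose described as established in six children, when it may rest on three, would be credited with precision it does not have. The description of the result as optimal adds to this, because only DLT counts drive the escalation.

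**Working it through.** **Reproducing 9 to 12.** Take a 3+3 in which the declared dose is always brought to six, returning to low where necessary:

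- low 0/3, high at most 1/6: 3 + 6 = 9, six at high
- low 0/3, high at least 2/3, three more at low: 3 + 3 + 3 = 9, six at low if it passes
- low 0/3, high at most 1/3 and then at least 2/6, three more at low: 3 + 6 + 3 = 12, six at low if it passes
- low 1/6, high at least 2/3: 6 + 3 = 9, six at low
- low 1/6, high filled to six: 6 + 6 = 12, six at high or low

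Every path that identifies a dose has 9 or 12 patients and six at that dose. Section 10.2 is therefore right for that design, but sections 2.2 and 5.1 do not specify it.

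**Applying the rules as written in 5.1 and 10.4.** Three paths leave a dose resting on three children:

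- **A.** Low 1/3 then 0/3 (1/6), high 0/3 in Cohort 3. Nine dosed, high on three. Section 5.1 accepts this final state explicitly.
- **B.** Low 0/3, high at least 2/3 in Cohort 2. The Cohort 3 condition in 5.1 is not met, so the trial ends at six with low seen in three.
- **C.** Low 0/3, high at most 1/3 in Cohort 2, reaching at least 2/6 in Cohort 3. Section 10.4 stops at nine with low seen in three. No step in the text returns to low.

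**Precision.** With 0 events in n, the exact two-sided 95% upper limit is 1 − 0.025^(1/n): 0.708 for n = 3 and 0.459 for n = 6.

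**Probabilities.** The protocol gives no DLT rates, so the rates below are assumptions. Write L and H for the low- and high-dose results in one cohort of three, with binomial probabilities:

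- P(A) = P(L=1) × P(L=0) × P(H=0)
- P(B) = P(L=0) × P(H≥2)
- P(C) = P(L=0) × [P(H=0) × P(H≥2) + P(H=1) × P(H≥1)]

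At 10% low and 20% high:

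- P(L=0) = 0.9³ = 0.729; P(L=1) = 3 × 0.1 × 0.9² = 0.243
- P(H=0) = 0.512; P(H=1) = 0.384; P(H≥2) = 0.104; P(H≥1) = 0.488
- P(A) = 0.243 × 0.729 × 0.512 = 0.0907
- P(B) = 0.729 × 0.104 = 0.0758
- P(C) = 0.729 × (0.512 × 0.104 + 0.384 × 0.488) = 0.1754
- A + B + C = 0.342; A + C = 0.266

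| Low/high DLT rate (assumed) | A | B | C | A+B+C | A+C |
|---|---|---|---|---|---|
| 5/10% | 8.5% | 2.4% | 7.4% | 18% | 16% |
| 10/20% | 9.1% | 7.6% | 17.5% | 34% | 27% |
| 10/30% | 6.1% | 15.7% | 26.5% | 48% | 33% |
| 10/40% | 3.8% | 25.7% | 30.2% | 60% | 34% |

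A+C applies if section 2.2 is read as sending Cohort 3 to low after high fails in Cohort 2, so that path B no longer leaves low on three.

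**The case against.** Only path A is written out in the protocol. Paths B and C treat low as the dose left standing on three children, which no sentence says. Sections 10.2 and 10.4 refer those endpoints to Figure 1, which was not available here and may contain a return to low. Path B also depends on reading 5.1 over 2.2. These points stand. They are why the 18 to 60% range is conditional, and why A and A+C are shown separately. They do not remove the problem: path A contradicts 10.2 on the text alone, and a fill-to-six step in Figure 1 would itself conflict with the final state accepted in 5.1.

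A reader might infer more than the documents support:

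- **A stop with two DLTs among six at low disproves the nine.** It does not. The sentence concerns the number needed to identify an MTD; a safety stop identifies none, and 10.2 provides for it separately.
- **Losses before infusion leave the trial short of nine dosed.** Section 8.12 allows a replacement for anyone who withdraws before infusion, or within four weeks without a DLT. The losses in the cited kidney trial concern a blood-derived product and do not give a rate for this one.
- **Dependence on new funding for patients 10 to 12 is an error.** Sections 2.2 and 5.1 disclose it openly.
- **The trial wrongly claims a true MTD.** Section 10.2 already limits the MTD to the two potential doses. What remains is the looser word optimal, which no activity criterion in the rules supports.

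**Conclusion.** The point holds: 10.2 states two design properties that the 5.1 rules do not deliver. The contradiction over six patients at the selected dose needs no assumption. The contradiction over the minimum of nine rests on path B and on the Cohort 3 condition in 5.1; section 2.2 can be read otherwise, so the passages must be reconciled.

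Under the assumed DLT rates, the explicit path occurs in about 4 to 9% of trials. All paths together leave a dose resting on three children in 18 to 60% on the 5.1 reading, or 16 to 34% if Cohort 3 goes to low. The totals assume that low is the dose carried forward in path C (and in path B where counted) and that Figure 1 adds no further step.

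**What to change.** Reconcile sections 2.2, 5.1, 10.2 and 10.4 and Figure 1, so that each Cohort 2 and Cohort 3 outcome has one stated consequence, including what follows when high fails after 0/3 at low. Which rule applies is for the sponsor to decide.

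If the 5.1 rules stand, restate 10.2 to say:

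- the selected dose may rest on 3 or 6 participants;
- a dose may be left as the only tolerated one with 6, 9 or 12 dosed in total;
- the DLT rate at that dose will be reported with its exact 95% confidence interval.

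If six at the selected dose is the intended property, 2.2 and 5.1 have to contain the steps that produce it.

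In either case, describe the result as the highest tolerated of the two dose bands rather than the optimal dose.

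If the 5.1 rules stand, the cost is protocol wording and a less favourable statement of precision, with no additional patients.

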10.3 Interim analyses

Safety data will be reviewed after dosing of the first and last patient of each cohort, with interim analyses provided to the DMC in order for decisions related to the next patient cohort to be made.

10.4 Criteria for the termination of the trial

The trial will be stopped when 2 patients out of 6 receiving the same dose level (2 cohorts) experience a DLT. At this point, either a MTD will be identified (green endpoints in Figure 1) or the trial will be stopped for safety (red endpoints in Figure 1).

10.5 Inclusion in Analysis

All eligible participants recruited will be analysed.

ATT-Heart Protocol - V1.0 (28-NOV-2024)

IRAS Number: 1008875 / EudraCT Number: XXXXX

11 Data Management

11.1 Source Documents

Source documents are original documents, data, and records from which participants' CRF data are obtained. These include, but are not limited to, hospital records (from which medical history and previous and concurrent medication may be summarised into the CRF), clinical and office charts, laboratory and pharmacy records, diaries, microfiches, radiographs, and correspondence.

All documents will be stored safely in confidential conditions. On all study-specific documents, other than the signed consent, the participant will be referred to by the study participant number/code, not by name.

11.2 Direct access to source data / documents

Only members of the trial research team and authorised representatives from the sponsor will have direct access to the source data and trial documentation. All source data and trial documentation will also be available to external auditors if and when required, and inspectors in the event of regulatory inspection. Access to the final data set will remain with the Chief Investigator.

11.3 Data recording and record keeping

The Chief Investigator will act as custodian for the trial data. The following guidelines will be strictly adhered to:

- Patient data will be pseudo-anonymised.
- All trial data will be stored in line with the *Medicines for Humans Use (Clinical Trials)* Amended regulations 2006 and the Data Protection Act 2018 (and all amendments to follow).
- All trial data will be archived in line with the Medicines for Humans Use (Clinical Trials) Amended regulations 2006 and as defined in the Sponsor's Archiving SOP (and all amendments to follow).

An electronic Case Report Form (eCRF) will be designed using the REDCap database which is fully validated and regulatory compliant. This is a web-based platform for electronic data capture. The eCRF will be designed in collaboration with the trial statisticians and trial team.

11.4 Archiving

Archiving will be authorised by the Sponsor following submission of the end of study report. Essential documents will be retained for a **minimum** of 25 years after completion of the trial. These documents will be retained for longer if required by the applicable regulatory requirements.

For Advanced Therapy Medicinal Products:

Records related to traceability of the IMP at site along with the patient identifiers will be retained at site for at least 30 years after the expiry date of the product or longer if required by the clinical trial authorisation. This will include the relevant documentation contained in the sponsor and investigator files as well as the trial participants' medical records.

12 Oversight Committees Involved in Trial

12.1 Data Monitoring Committee (DMC)

This study will use an External Data Monitoring Committee (E-DMC).

The DMC will be responsible for on-going monitoring of the efficacy and safety of subjects in the study according to the DMC Charter. The DMC charter will detail membership and terms of reference.

In order to ensure patient safety throughout the conduct of the trial, the DMC will review and evaluate accumulated safety data, study conduct and progress. The DMC will make the decisions about the continuation, modification or termination of the study. The recommendations made by the DMC to alter the conduct of the study will be forwarded to the Sponsor for final a decision. The Sponsor will forward such decisions to regulatory authorities, as appropriate.

Outside of the planned reviews, a DMC meeting could be triggered if specific safety events occur (as stated below):

- If a DLT is observed in two patients within a dosing cohort.
- If death of a patient infused with TR006 occurs.
- Or at any other time deemed necessary by the DMC chair.

The DMC will develop its own operation procedures in consultation with the sponsor which will be documented in the DMC charter.

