4.2 Risks associated with the administration of the Treg cell product

The potential risks associated with Treg therapy can be categorised as immunological, physiological, infectious, or due to adverse interactions with other treatments. While the single ascending dose design combined with safety reviews after the first and last dose of each dosing cohort, should minimise these risks, it is nonetheless necessary to consider the potential risks in turn.

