8.12 Participant Withdrawal Criteria

Participants have the right to withdraw from the study at any time for any reason. The investigator also has the right to withdraw patients from the study in the event of inter-current illness, AEs, SAE's, SUSAR's, protocol violations, cure, administrative reasons or any other reasons deemed appropriate. It is understood by all concerned that an excessive rate of withdrawals can render the study un-interpretable; therefore, unnecessary withdrawal of patients should be avoided. Should a patient decide to withdraw from the study, all efforts will be made to report the reason for withdrawal as thoroughly as possible.

As the IMP in this trial is an advanced therapy with a single infusion, participants who wish to withdraw from trial after IMP has been administered, will be asked to confirm whether they are still willing to attend the safety follow up visits as per protocol for the duration of the trial. If participants are not willing to do this, consent will be sought for the trial team to access routine data collected from hospital/GP visits for the duration of the safety follow up period.

In situations where a patient has to be withdrawn or decides to withdraw from the study, an additional patient may be recruited and dosed if:

- They withdraw prior to the TR006 infusion.
- They withdraw during their 4-week follow-up period, and have not yet experienced a DLT.

If a patient withdraws from the trial a withdrawal form in the study database will be completed.

The DMC will review all patients, including any withdrawn patients, to determine if a primary outcome has occurred (DLT, no DLT or DLT not determined in the active period).

In the following situations, the withdrawn patient will have contributed to the primary outcome and no additional patient will be recruited:

- If they withdrew after they completed their 4-week follow-up safety period.
- If they experience a DLT during their 4-week follow-up safety period, which may or may not be the reason for withdrawal.

9 Assessment of Safety

Definitions

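### The unscheduled DMC trigger counts DLTs per dosing cohort while the stop counts them per dose level, so in an expansion cohort a suspected second DLT in child 2 brings no DMC review due before child 3

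*Protocol*

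**What the plan says.** Three rules in the protocol meet at this step.

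- **The stop (10.4, repeated in 10.2).** "The trial will be stopped when 2 patients out of 6 receiving the same dose level (2 cohorts) experience a DLT". The unit is the dose level.
- **The unscheduled DMC meeting (12.1).** Outside planned reviews, a meeting may be called "If a DLT is observed in two patients within a dosing cohort", after the death of an infused patient, or whenever the chair sees need. The DLT item is counted by dosing cohort, and the wording of the list is permissive.
- **The planned reviews (10.3).** "Safety data will be reviewed after dosing of the first and last patient of each cohort". Section 4.2 describes "safety reviews after the first and last dose of each dosing cohort", which ties the term dosing cohort to the unit reviewed at those two points.

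Within a cohort, 5.1 sets a gap of at least four weeks after the first child. Then: "After safety of the treatment is confirmed for the first patient, the second and third patients of this cohort will receive the same dose". No interval is set between the second and third, and 10.2 applies the same process to Cohorts 2 and 3.

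A second cohort at one dose can arise in two ways within the nine planned children. At the low dose, "If a DLT occurs in the Cohort 1, the next cohort of 3 patients will be administered to the same dose" (10.2). At the high dose, 5.1 lets Cohort 3 go ahead when Cohort 2 had no more than 1/3 DLTs. A third way is the extension to 12 children.

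On who decides, 8.12 says: "The DMC will review all patients, including any withdrawn patients, to determine if a primary outcome has occurred". Section 5.1 requires a DLT to be judged related to TR006.

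**The concern.** In the first cohort at a dose, the per-cohort and per-dose counts are the same. In an expansion cohort after 1/3, one DLT already stands at the dose, so the stop is met at that cohort's first DLT. At that moment the 12.1 count for the cohort is one, and the trigger is not met.

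An event in child 1 or child 3 is picked up by a planned review. An event in child 2 is not: the next planned review follows child 3.

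An expansion cohort exists to find out whether a second DLT appears. A DLT needs a judgement of relatedness, and 8.12 gives the DMC the task of determining it. While that judgement is pending for child 2, nothing in 12.1 calls for the DMC to meet or for dosing to wait. At stake is the infusion of one further child at a dose that may already have met its stopping rule, with a product that 9.2 describes as not previously tested in humans (8.8 says not extensively tested).

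**Working it through.** **1. The plan's own figure.** Section 10.2 states 9 to 12 patients. The completed paths are 3 low + 6 high = 9, 6 low + 3 high = 9, and 6 low + 6 high = 12. (A safety stop at the low dose ends at 6 or fewer.) The stated range is reproduced, and the paths show where a second group of three is dosed at one level.

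**2. The counts in an expansion cohort after 1/3, at the cohort's first DLT.**

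| First DLT of the cohort in | DLTs at the dose (10.4 stops at 2) | DLTs in the cohort (12.1 needs 2) | Planned review before the next infusion? |
|---|---|---|---|
| child 1 | 2 | 1 | yes |
| child 2 | 2 | 1 | **no** |
| child 3 | 2 | 1 | yes, after the last child |

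Only the child 2 row lacks a DMC review.

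**3. How often that row arises.** The protocol gives no DLT rate, so p is an assumption: constant, independent between children and equal at both doses, with q = 1 − p. I use 1/9, 1/6 and 1/3. The lowest is one infusion-related event among nine adults in the liver transplant trial in section 1.4; the other two are chosen to show a range.

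Given an expansion cohort after 1/3:
- stop reached: 1 − q³
- first DLT in child 2: q × p

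Over the whole trial, the paths add up:
- low-dose expansion: 3pq² × qp = 3p²q³
- high dose in Cohorts 2 and 3: q³ × 3pq² × qp = 3p²q⁶
- high dose in patients 7 to 12: 3pq² × q³ × 3pq² × qp = 9p³q⁸

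| | p = 1/9 | p = 1/6 | p = 1/3 |
|---|---|---|---|
| 1 − q³ | 29.8% | 42.1% | 70.4% |
| qp | 9.9% | 13.9% | 22.2% |
| qp / (1 − q³) | 33% | 33% | 32% |
| 3p²q³ | 2.6% | 4.8% | 9.9% |
| 3p²q⁶ | 1.8% | 2.8% | 2.9% |
| 9p³q⁸ | 0.5% | 1.0% | 1.3% |
| Sum over the trial | 4.9% | 8.6% | 14.1% |

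At p = 1/6, for example: qp = 5/36 = 13.9%; 1 − 125/216 = 42.1%; and 0.0482 + 0.0279 + 0.0097 = 0.0858.

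These are upper bounds on how often the gap arises. They count every first DLT in child 2, including those recognised at once as DLTs and those that become known only after child 3 has been infused. The last path needs funding not yet obtained. Section 2.2 also describes it as enlarging one cohort to six; on that reading the 12.1 count would be right there, and the sum at p = 1/6 falls to 0.0482 + 0.0279 = 7.6%.

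**The case against.** The strongest reply is that 10.4 is unconditional. If child 2's DLT is established, the trial stops and infusing child 3 would breach the protocol, with or without a DMC meeting. If nothing is yet suspected in child 2, no trigger of any wording would fire. This stands, and it removes most of the apparent harm. What remains is the interval between suspicion and determination, because a DLT needs a relatedness judgement that 8.12 gives to the DMC.

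A second reply is that cohort is used loosely. Sections 2.1 and 4 speak of expanding the lower-dose cohort, and 2.2 of expanding a cohort to six. If dosing cohort means everyone at a dose, the two counts agree. Sections 4.2, 5.1 and 10.3 favour groups of three, so the point is conditional on that reading. If the dose-level count was intended, 12.1 should say so.

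Third, oversight exists nearby. The DMC reviews after child 1 of the expansion cohort, knows that one DLT stands, and could ask for a hold then. SAEs reach the sponsor's R&D office within 24 hours (9.4), and the chair may convene at any time. All of this is true, but none of it makes a review due at this step. Figure 1 and the DMC charter were not available here and may cover it.

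A reader might infer that the protocol lets dosing continue after a confirmed second DLT. It does not. A reader might also infer that children 2 and 3 must be four weeks apart. Leaving them unspaced is a stated design choice, and a compulsory gap would press on each child's own 3 to 6 month infusion window. Any count of avoidable infusions would measure that spacing rather than the trigger, and would need an accrual rate that the protocol does not give.

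**Conclusion.** The mismatch of units holds if dosing cohort means the group of three. Its effect is confined to one situation: an expansion cohort after 1/3 at that dose, child 1 without a DLT, and a suspected but undetermined DLT in child 2. There the stop may have been met and no DMC review is due before child 3.

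Under the assumed common rate of 1/6, the gap arises in 13.9% of such cohorts and at most 8.6% of trials (4.9% to 14.1% for rates of 1/9 to 1/3). The dose finally selected is the same either way. Minor.

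**What to change.** In 12.1, replace the DLT item with:

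*If a second DLT is suspected at the same dose level, counted across cohorts; dosing at that dose pauses until the DMC has met.*

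Carry the same line into the DMC charter. In the first cohort at a dose the count is unchanged, because a second DLT at the dose is also the second in the cohort. In an expansion cohort, a suspected DLT in child 2 then leads to a DMC determination before child 3.

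The cost is one line and no extra data. Nobody is delayed unless a second DLT is suspected; in that case the next child waits for one DMC meeting, to be arranged with that child's 3 to 6 month window in mind. The line cannot help where child 3 has been infused before anything is suspected in child 2. No change to the spacing of children 2 and 3 is proposed.
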